8.4.4.5. MRI Scan procedures

Monitor subject with ECG and/or pulse oximetry and verbal communication.

Setting up Pulse Oximetry and/or ECG

Set up pulse oximetry and/or an ECG per standard of care. Place the oximetry clip on the subject's finger or other any other appendage that results in valid pulse oximetry readings. Or, position MRI compatible surface electrodes on the subject to ensure the subject's heart rate can be continuously monitored during the scan. During the MRI scan, periodically record heart rate, and blood oxygen saturation levels. Visually examine the ECG during the MRI scan. After the MRI scan, remove the subject from the MRI field.

MRI Scan

After confirmation by the electrophysiologist or device specialist that all pre-MRI system checks (mentioned above) have been met, subjects will have their MRI scan completed by a radiology staff member. **Note:** If the subject does not pass the Pre-MRI scan System Check specified above, then the subject should not undergo an MRI scan. The subject can be rescheduled to come back to repeat the Pre-MRI scan System Check testing within the visit window.

Protocol required MRI scan sequences for each subject undergoing an MRI scan are described in detail in the MRI Scan Guidelines. It is recommended that the MRI scan be set up on the MRI scanner in advance of the first subject scheduled for a study scan to ensure the scan has been appropriately programmed and to provide adequate time to address any questions or issues that may arise.

Subjects will undergo two different scans for the study, both of which will expose the ICD/ CRT-D to extreme scanning conditions: (1) a thoracic scan that is RF intensive, and (2) a head scan that is gradient intensive. The thoracic scan should be set up to last about 6 minutes and 15 seconds, and the head scan should be set to get as close as possible to 5 minutes without being under 5 minutes. The thoracic scan will need to be repeated 4 times to ensure the subject is scanned approximately 25 minutes. Further details about the set-up, programming and ways to adjust the parameters for MRI scans can be found in the MRI Scan Guidelines.

The subject may be in the bore or near the vicinity of the magnet for approximately 60 minutes. The actual amount of time the subject will be scanned is about 30 minutes: 25 minutes for the thoracic scan, and 5 minutes for the head scan.

These two MRI scans are not intended to be diagnostic in nature and therefore the administration of contrast fluids or sedation, or the application of water and fat saturation techniques are not permitted.

Consult the “MRI Ready Systems Manual. MRI Procedure Information for the St. Jude Medical™ MR Conditional System” for guidelines and ‘precautions related to conducting an MRI scan with the implanted study ICD/ CRT-D system.

NOTE: The study MRI scan is being performed to demonstrate safety and MRI compatibility of the ICD/ CRT-D system being evaluated in this trial for an MRI scan, and is not meant to be diagnostic in nature. The MRI scan will not be read by the radiologist.

If subject movement causes distortion on the MRI, do not repeat.

An optional non-study MRI scan sequence may be conducted at the request of the subject and discretion of the Investigator and radiologist. This optional non-study MRI scan sequence must be done in accordance with the guidelines and precautions in the MRI Ready Systems Manual.

Cardiac Monitoring

During the entire MRI scan, the subject’s cardiac function must be monitored using pulse oximetry and/or ECG by a study trained electrophysiologist, cardiologist capable of delivering external cardiac pacing defibrillation and advanced cardiac life support. Verbal communication with the subject must also take place to assess and/or confirm any clinically significant changes noted in the subject’s oxygen saturation or heart rate, as well as any clinically significant complaints not obvious with pulse oximetry; record these changes and complaints during the MRI scan.

Advanced cardiac lifesaving procedures must be in place to address situations where a life-threatening arrhythmia and/or hemodynamic collapse occurs. The programmer must be used outside the American College of Radiology (ACR) defined Zone 4 magnet room. If the subject’s hemodynamic function is compromised during the MRI scan, discontinue the MRI procedure and take proper measures to restore the subject’s hemodynamic function.

Handling of Subjects Unable to Tolerate an MR Scan

In cases where the scan cannot be tolerated by the subject, remove the subject from the scanner. Assess the subject for possible adverse events and treat the subject’s reported symptoms according to your institution’s standard of practice. Document the reason for the intolerance. At a minimum, information related to the sequence used to perform the scan, the length of time the subject was scanned, and the whole-body SAR level reached should be collected and submitted to Abbott. A repeat scan is not required to be completed but may be rescheduled. The subject is not withdrawn from the study. The subject should be scheduled to return for their 1-month post MRI scan visit.

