Baseline/ MRI Scan Visit	
45 (+7) days after implantation or after most recent lead revision
 
MRI scan should occur within 14 days of Baseline visit.
 
The pre-MRI scan, MRI, and post MRI scan procedures should occur on the same day.
	
Pre-MRI Scan testing
 
 Assess inclusion/exclusion criteria Screen, clear and prep subject for MRI scan Complete MRI screening form Complete MRI Hazard Checklist Administer pregnancy test – can be done up to 7 days before MRI scan Interrogate device Perform capacitor maintenance Obtain in-clinic lead measurements: bipolar capture, sense, pacing and HVLI impedances^{1,2} Setup and activate MRI Settings 
During MRI Scan
 
 Monitor subject with ECG, or pulse oximetry, and verbal communication 
Post-MRI scan testing
 
 Interrogate device Deactivate MRI Settings Obtain in-clinic lead measurements: bipolar capture, sense, pacing and HVLI impedances^{1,2} Evaluate subject for any adverse events (serious and non-serious) and submit an AE CRF (as applicable). Report deviations, screening failure/withdrawal and out of service as applicable Submit MRI scan results, e.g. scan time, sequences used, etc. Upload device session records through the EDC study site portal
1-Month Post MRI Scan Visit	30 days after MRI scan (0/+14 days)	
 Interrogate device Obtain in-clinic lead measurements: bipolar capture, sense, pacing and HVLI impedances^{1,2}

Study Visit	Visit Window	Study Procedures and Data Collection
		
 Evaluate subject for any adverse events and submit an AE CRF (as applicable). Report deviations, withdrawal and out of service as applicable Upload device session records through the EDC study site portal
System Revision (if applicable)	Can occur any time after implant	
 Interrogate device Obtain applicable in-clinic lead measurements: bipolar capture¹, sense², and pacing and HVLI impedances for cases where the lead was repositioned, or was replaced with another Durata/Optisure or Tendril/Isoflex, Quartet lead, or where the ICD/ CRT-D was replaced with another Ellipse ICD/ Quadra Assura MP CRT-D. Evaluate subject for any adverse events and submit an AE CRF (as applicable). Report deviations, withdrawal and out of service as applicable Upload device session records through the EDC study site portal

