
*Note: When MRI Settings are enabled, sensing is disabled. Determine whether or not the subject requires pacing support during the MRI scan. When pacing support is needed, set the MRI Mode to the asynchronous pacing mode (VOO). When pacing support is not needed, set the MRI Mode to Pacing Off.
 
Some subjects may be susceptible to cardiac arrhythmia induced by competitive pacing when an asynchronous MRI Mode is selected. For these subjects, it is important to select an appropriate MRI pacing rate to avoid competitive pacing and then minimize the duration of the asynchronous pacing operation.
 
In MR Conditional ICDs, tachytherapy is disabled when the MRI settings are programmed. After the electrical measurements for the RA lead and/or RV lead have been taken, capacitor maintenance has been performed, the MRI Checklist (on the programmer) verified and the MRI Setting saved, activate the MRI parameters.
		

TABLE 6: MRI PARAMETERS- CRT-D

Parameters	Selectable Options	Nominal Values
MRI Mode*	DOO Pacing off	DOO
MRI Base Rate	30-100 bpm	85 bpm
MRI paced AV delay	25-120ms	120 ms
MRI RV Pulse Configuration	Bipolar	n/a
MRI RV Pulse Amplitude	5.0 V, 7.5V	n/a
MRI RV Pulse Width	1.0 msec	n/a
MRI V pacing chamber	RV only	RV only
Tachy settings	Disabled	Disabled

*Note: When MRI Settings are enabled, sensing is disabled. Determine whether or not the subject requires pacing support during the MRI scan. When pacing support is needed, set the MRI Mode to the dual chamber asynchronous pacing mode (DOO).
 
Some subjects may be susceptible to cardiac arrhythmia induced by competitive pacing when an asynchronous MRI Mode is selected. For these subjects, it is important to select an appropriate MRI pacing rate to avoid competitive pacing and then minimize the duration of the asynchronous pacing operation.
 
In MR Conditional CRT-Ds, tach therapy is disabled when the MRI settings are programmed.
 
After the electrical measurements for the RA lead and/or RV lead, and/or LV lead have been taken, capacitor maintenance has been performed, the MRI Checklist (on the programmer) verified and the MRI Setting saved, activate the MRI parameters.
		

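### The protocol's rhythm-monitoring duty ends with the MRI scan, but tachytherapy stays off until the MRI Settings are disabled afterwards

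*Combined protocol and SAP*

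**What the plan says.** **Monitoring.** Section 8.4.4.5, under Cardiac Monitoring, sets a duty that applies "During the entire MRI scan". On method and staff it says: "cardiac function must be monitored using pulse oximetry and/or ECG by a study trained electrophysiologist, cardiologist capable of delivering external cardiac pacing defibrillation". Table 4 lists "Monitor subject with ECG, or pulse oximetry, and verbal communication" in its scan block and has no monitoring line in the pre-scan or post-scan blocks. The set-up text in 8.4.4.5 asks that the "heart rate can be continuously monitored during the scan". The mitigation column of Table 10 also limits continuous monitoring to the scan. Table 3 ticks ECG and optional oximetry only in the MRI Period column.

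**Therapy.** The notes to Tables 5 and 6 say that sensing is off while the MRI Settings are enabled. On therapy they say: "In MR Conditional ICDs, tachytherapy is disabled when the MRI settings are programmed" and "In MR Conditional CRT-Ds, tach therapy is disabled when the MRI settings are programmed". Table 4 places "Setup and activate MRI Settings" in pre-scan testing. Section 8.4.4.6 gives the order after the scan: out of the bore, interrogate, disable the settings. It warns in bold that tachyarrhythmia therapy comes back only through that last step. Section 8.4.4.5 adds: "The programmer must be used outside the American College of Radiology (ACR) defined Zone 4 magnet room".

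**The concern.** Every subject has an indication for an ICD or CRT-D. While the MRI Settings are active the device neither senses nor treats VT/VF, so rescue depends on someone seeing the arrhythmia. The CIP recognises this and assigns a qualified clinician, but ties that duty to the scan and not to the time without therapy. A site working from the CIP text alone could take a subject out of the magnet room with therapy off and nobody required to watch the rhythm.

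Loss of tachytherapy applies to all subjects. Competitive pacing, which Table 10 lists as a possible trigger of VT/VF, applies only in an asynchronous mode. That mode is nominal for the CRT-D (DOO, Table 6) but not for the ICDs (Pacing off, Table 5). The issue is subject safety, not estimation.

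**Working it through.** **Comparing the two spans**

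| Stage | Tachytherapy | Rhythm monitoring the CIP requires |
|---|---|---|
| Settings activated, subject taken to the scanner | Off (8.4.4.4) | None under Table 4 and 8.4.4.4; required if the Table 3 MRI Period begins at activation |
| Scan | Off | Yes (8.4.4.5, Tables 3, 4 and 10) |
| Out of the bore, moved to where the programmer may be used, interrogated | Off (8.4.4.6) | None stated |
| Settings disabled | On | Not at issue |

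The third row is the firm finding. Tables 3 and 4 and section 8.4.4.6 all place deactivation in post-scan testing, and none of them carries ECG or oximetry into that stage. Section 8.4.4.3 treats the scan and the post-scan testing as separate parts of the visit, so the word scan cannot simply be stretched to cover both.

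The first row is arguable. Table 4 and 8.4.4.4 put activation before the scan. Table 3, as extracted, ticks activation in the same column as ECG.

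**Time.** Section 8.4.4.5 gives four thoracic scans of 6 min 15 s and a head scan of 5 min: 4 × 6.25 + 5 = 30 min, which matches its stated total. It also gives about 60 min in or near the magnet, so 60 − 30 = 30 min are spent there without active scanning. The CIP does not say whether the monitoring duty covers the 30 or the 60 min. Nor does it give the time from activation to arrival at the magnet, or from leaving it to disabling.

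For illustration only, assume that the settings are active for all 60 min and that 0 to 30 min are added on each side:
- Therapy-off time: 60 + 0 + 0 = 60 to 60 + 30 + 30 = 120 min.
- Outside active scanning: 60 − 30 = 30 to 120 − 30 = 90 min.
- Outside the monitored period, if the duty covers the full 60 min: 0 to 60 min, of which 0 to 30 min fall after the scan.

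**Subjects.** Section 8.1.12 plans 4 × 15 = 60 as a minimum and anticipates attrition of 4 × 5 = 20, leaving 40. So 40 subjects (all attrition before activation) to 60 (none before activation) would have therapy switched off. Of these, Group 4 contributes 15 − 5 = 10 to 15, with an asynchronous nominal mode. Groups 1 to 3 contribute 3 × 10 = 30 to 3 × 15 = 45, with pacing nominally off. Enrolment is a minimum, so true numbers may be higher.

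**The case against.** The strongest reply is that the CIP is not the only instruction to sites. Section 8.4.4.5 sends them to the MRI Ready Systems Manual for precautions, and that manual may require monitoring for as long as the settings are active. This cannot be checked here. It limits the finding to what the CIP itself states.

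Other points have some force:
- The opening line of 8.4.4.5 on monitoring carries no time limit of its own. It stands under a scan heading, though, and the paragraphs that follow limit the duty to the scan.
- The requirement for advanced life support to be ready is not confined to the scan. It calls for readiness to respond, not for anyone to watch the rhythm. The attention to symptoms just after the scan in 8.4.4.6 is likewise not rhythm monitoring.
- Staff are present for the programmer steps, and 8.4.4.6 lists removal, interrogation and disabling as consecutive steps with no planned wait. The exposed time is therefore mainly transfer and any waiting, and may be short.

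A reader might infer more than the documents support:
- **An unambiguous gap on both sides of the scan.** Table 3 leaves the pre-scan side open to interpretation.
- **Planned unmonitored intervals.** Section 2.3 counts delays in reprogramming, if any, which is outcome reporting. Table 7 deals with documentation and withdrawal, so the lack of clinical steps there is weak evidence. Both only show that the scan-based wording does not reach cases where disabling is late or the scan is not completed.
- **A threat to the safety endpoint.** Safety surveillance starts once the MRI Settings have been programmed (sections 8.3.2 and 16.1), so events in the gap are still reportable.

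**Conclusion.** The point holds, in limited form. In the CIP as written, the required monitoring ends with the scan while tachytherapy remains off until the settings are disabled. The post-scan gap is clear. The pre-scan gap depends on how the Table 3 MRI Period is read.

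The size of the gap cannot be derived: the only stated times are about 30 min of scanning within about 60 min in or near the magnet, and the wider ranges above rest on assumed transfer times. The 40 to 60 subjects are simply those expected to have the settings activated.

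Confidence is medium, because the cited manual was not available. The correction should be made: the scan is non-diagnostic, section 15.7 allows that subjects may gain no direct benefit, and the remedy is cheap.

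**What to change.** In 8.4.4.5, Cardiac Monitoring, replace "During the entire MRI scan" with: *From activation of the MRI Settings until they are disabled and tachytherapy is confirmed on, including transfer and any scan not started or stopped early*. Keep the same clinician qualification and require external defibrillation to be available throughout.

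Use the same span in:
- the oximetry/ECG set-up text of 8.4.4.5;
- the ECG and oximetry rows of Table 3;
- the monitoring line of Table 4;
- the mitigation column of Table 10.

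Add *keep monitoring until the MRI Settings are disabled and tachytherapy is confirmed on* to the part of 8.4.4.5 on subjects who cannot tolerate the scan, and to the Table 7 row for settings programmed but scan not completed.

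If the manual already requires this span, state the requirement in 8.4.4.5 with the citation; the existing general reference does not tell sites what the span is.

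Cost: the existing clinician and portable monitoring and defibrillation equipment must also cover transfer. The change needs a CIP amendment, ethics committee approval before it takes effect (sections 17.2 and 23) and site retraining. No endpoint, sample size or analysis changes.

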8.1.12. Number of subjects required for clinical study

A minimum of 60 total subjects will be enrolled in this study. Fifteen (15) subjects for each of the 4 main device groups (See **Figure 1**) will be enrolled in this study to meet the minimum required 10 subjects per device arm, as requested by the NMPA for each group accounting for attrition of anticipated 5 subjects for each group in this study.

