8.2.1. Description of the effectiveness endpoints

- Proportion of leads with a capture threshold increase of $\leq 0.5V$ at 0.5ms for RA and RV leads and $\leq 1.0V$ at 0.5ms for LV leads from pre-MRI scan to 1-month post-MRI scan testing.
- Proportion leads with a sensing amplitude decrease of $\leq 50\%$ from pre-MRI scan testing to 1-month post-MRI scan.

8.2.2. Selection of method and time for evaluation, recording and analysis of the effectiveness endpoints

Since the objective is to evaluate the effect of MRI exposure for the ICD/ CRT-D device groups included in this study, the effectiveness parameters were selected to compare abnormal changes in device performance from pre- to 1-month post- MRI scan. The pre-MRI measurements are collected within the same day prior to the MRI scan. The 1-month post-MRI scan measurements are collected at 30 days post-MRI scan (within +14 days) to ensure any effect of the MRI exposure is captured.

The effectiveness parameters are recorded directly from the device. The device measurements will be obtained using the Merlin programmer to interrogate the device during study visits. The analysis of the effectiveness parameters will be conducted on all subjects with complete data from pre- to 1-month post-MRI scan.

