2.4 Sample Size Calculations

There is no hypothesis testing is planned in this study, and no sample size calculation or power analysis has been performed.

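### As visibly written, leads from scans stopped early can enter both effectiveness proportions, and no visible rule says which pre-scan reading is the reference after a repeat scan.

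*Combined protocol and SAP*

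**What the plan says.** **Planned exposure.** CIP 8.4.4.5 specifies an RF-intensive thoracic scan of about 6 min 15 s and a gradient-intensive head scan of at least 5 minutes. On the thoracic scan: "The thoracic scan will need to be repeated 4 times to ensure the subject is scanned approximately 25 minutes". Total scan time is put at about 30 minutes.

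**Scan not tolerated.** The same section removes the subject from the scanner and requires the sequence, scan time and whole-body SAR to be submitted. It then says: "A repeat scan is not required to be completed but may be rescheduled. The subject is not withdrawn from the study". The 1-month visit is still to be scheduled.

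**Who is analysed.** CIP 8.2.2: "The analysis of the effectiveness parameters will be conducted on all subjects with complete data from pre- to 1-month post-MRI scan".

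**Reference reading.** CIP 8.2.2: "The pre-MRI measurements are collected within the same day prior to the MRI scan". CIP Table 4 also puts pre-scan testing, scan and post-scan testing on one day.

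**Withdrawal.** CIP Table 7 (8.4.5) withdraws a subject whose MRI settings were programmed but whose study scan was not completed. Its example is a change of mind.

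**SAP.** Sections 3.0 and 3.5 refer to an Analysis Cohort. Section 2.1 (populations) and the detail of 2.3.2 (effectiveness endpoints) are redacted. Section 2.9 addresses only discontinuation before the 1-month visit. Sections 2.8 and 2.13 plan no subgroup or exploratory analysis.

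**The concern.** The MRI exposure is the intervention, and both effectiveness proportions are meant to describe lead performance after that exposure. Two gaps weaken the link.

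1. A subject stopped part-way who attends the 1-month visit has complete data in the sense of 8.2.2. The leads then count in both proportions although they did not receive the specified exposure. If less exposure means less effect, the proportions move toward success.

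2. A rescheduled scan produces a second pre-scan reading, taken after a first, partial exposure. If that reading is the reference, any shift caused by the stopped scan is subtracted from the 1-month change.

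Stopped scans are foreseeable. CIP 8.4.4.5 allows about 60 minutes in or near the magnet and permits no sedation, and Table 11 lists claustrophobia as an unavoidable event. Groups are small, so a few such subjects weigh visibly in the results.

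**Working it through.** **The plan's own figures reproduce.** CIP 8.1.12 plans "Fifteen (15) subjects for each of the 4 main device groups", "to meet the minimum required 10 subjects per device arm", "accounting for attrition of anticipated 5 subjects for each group in this study". 10 + 5 = 15 per group and 4 × 15 = 60. Exposure: 4 × 6.25 min = 25 min thoracic, and 25 + 5 = 30 min in all. SAP 2.4 says "no sample size calculation or power analysis has been performed", so there is no power figure to rebuild.

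**Does a stopped scan meet the analysis rule?** A subject stopped after one thoracic run has 6.25/25 = 25% of the thoracic time, 6.25/30 = 21% of the total and no head scan. With a pre-scan reading and a 1-month reading, this subject satisfies 8.2.2 as written.

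**Dilution.** Assumptions, none of them from the documents:
- n = 10 evaluable subjects with one lead each;
- failure probability p after full exposure;
- k subjects under-exposed and wholly unaffected.

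Expected observed success = 1 − p(n − k)/n. Chance of seeing no failure = (1 − p)^(n − k).

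| p | k = 0 | k = 1 | k = 2 | k = 3 |
|---|---|---|---|---|
| 5%: observed success | 95% | 95.5% | 96% | 96.5% |
| 10%: observed success | 90% | 91% | 92% | 93% |
| 20%: observed success | 80% | 82% | 84% | 86% |
| 10%: chance of no failure | 34.9% | 38.7% | 43.0% | 47.8% |

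Each under-exposed subject adds p/10 to observed success, which is 0.5, 1 or 2 points for p = 5%, 10% or 20%.

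**Which reading is the reference after a repeat?** The same-day wording in 8.2.2 speaks of one scan and fits either visit. CIP 8.4.4.4 does re-anchor the 1-month visit to the visit at which the scan was completed. But that sentence concerns subjects who failed pre-scan device testing and had not yet been exposed. No visible text settles the case of a stopped scan followed by a repeat.

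**What the later reference could hide.** The shifts here are assumed.
- Capture, RA or RV lead (limit 0.5 V): a rise of 0.4 V after the stopped scan and 0.4 V after the repeat totals 0.8 V, a failure against the first pre-scan value. Against the repeat-visit value it reads 0.4 V, a success.
- Sensing (limit 50%): two successive losses of 40% give 1 − 0.6 × 0.6 = 64%, a failure against the first value. Against the second value the loss reads 40%, a success.

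The two illustrations assume opposite things about a stopped scan: no effect in the first, a real effect in the second. They are alternatives and must not be added.

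**Precision of a completed-scan set.** If all n leads succeed, with one lead per subject, the exact two-sided 95% lower limit is 0.025^(1/n). This gives 69.2% for 10/10, 66.4% for 9/9, 63.1% for 8/8 and 59.0% for 7/7.

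**The case against.** The strongest reply is that the plan may already deal with this. The SAP works with an Analysis Cohort and evaluable device data, and the sections that would define the cohort and detail the effectiveness endpoints are redacted. A reader might infer that stopped scans are analysed as if fully exposed, or that a repeat scan resets the reference. Neither is written anywhere. The documents support only that CIP 8.2.2 sets no exposure condition and that no visible text names the reference after a repeat. That part stands.

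Second, Table 7 may withdraw these same subjects, which would largely close the under-exposure route. Its example is a change of mind, so its reach is arguable, and 8.4.4.5 says the opposite for intolerance. This limits the certainty of the point but adds a conflict that has to be resolved.

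Third, there is no hypothesis test, success criterion or power calculation, so no error rate is affected. A reader might also say that the label claim rests on about ten subjects per group. CIP 8.1.2 does not support that, since these data supplement IDE data from the United States and Europe.

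Fourth, keeping everyone who was scanned is defensible. A scan can be stopped for hemodynamic compromise, so a completed-scan set selects those who tolerated it and may itself favour success. For that reason the documents do not support letting only full-exposure subjects count toward the ten per group. CIP 8.1.12 attaches no such condition to that number.

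Finally, CIP 8.4.4.4 requires capture thresholds to be stable before the MRI settings are saved. This is only a partial safeguard: no numerical meaning is given to stable, and the 2.5 V limit for RA and RV leads bounds the level, not the change.

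**Conclusion.** The concern holds in a limited form. On the visible text, partly exposed leads can enter both effectiveness proportions and dilute an MRI effect, and the reference after a repeat scan is open to a reading that absorbs part of the effect. Both the redacted SAP sections and Table 7 could narrow this.

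The size cannot be determined, because the documents give no rate of stopped or repeated scans. Under the stated assumptions, the dilution is about one to a few percentage points per group. A reset reference matters lead by lead, and only for subjects scanned twice. The point affects how well the descriptive proportions answer the trial's own question; it does not show that the results would be wrong. The change is still worth making, because the exposure data are already collected and no visible analysis uses them.

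**What to change.** In CIP 8.2.2 and the matching SAP sections:

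- **(a)** Keep the analysis of all scanned subjects. Beside it, report both effectiveness proportions for subjects who completed the full protocol scan. List delivered scan time, sequences and SAR by subject, and state the number of full-exposure subjects in each group.
- **(b)** For a subject re-scanned after a stopped scan, use the last measurement before the first exposure as the reference for the 1-month change, and count safety events from the first exposure.
- **(c)** Reconcile the intolerance paragraph of CIP 8.4.4.5 (subject not withdrawn) with Table 7 (subject withdrawn if settings were programmed and the scan was not completed), so that all sites handle a stopped scan in the same way.

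The cost is wording, one extra table and wider intervals in the completed-scan set: for example, a lower limit of 63.1% with 8/8 against 69.2% with 10/10. Because completing the scan may depend on how the subject or system responded, the completed-scan figures should stand beside the all-scanned figures and not replace them.
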